Appendix F Detailed Description of Amendments to Text

The primary sections of the protocol affected by the changes in Amendment No. 03 are indicated. The corresponding text has been revised throughout the protocol.

Change 1: Updated Appendix E Collection, Storage, and Shipment of Bioanalytical Samples.

The change occurs in [Appendix E Collection, Storage, and Shipment of Bioanalytical Samples](#):

Initial wording: Appendix E Collection, Storage, and Shipment of Bioanalytical Samples

3. Centrifuge the vacutainers for 10 minutes at approximately 1100-1300 relative centrifugal force (RCF) at approximately 4°C in a refrigerated centrifuge or at ambient temperature. Note: if using a collection device other than Becton-Dickinson, refer to manufacturer's instruction for proper centrifugation force and time.
4. Immediately following centrifugation, gently remove plasma from the packed cells. To ensure a more homogeneous sample, all plasma should first be transferred into 1 aliquot. From there, split the plasma evenly between the 2 aliquots. A minimum of approximately 1.2 mL needs to be obtained for each sample. Labeling may include protocol number (TAK-390MR_106), matrix (ie, plasma), analyte (TAK-390MR), enrollment number, nominal day and time, and either "SET 1" (for original sample) or "SET 2" (for duplicate sample).
5. Cap the labeled storage tubes and freeze the plasma samples immediately at approximately -20°C or lower. No more than 45 minutes will elapse between blood collection and freezing the plasma sample.

Instructions for processing and shipping of plasma samples for genotyping analysis

To be determined when laboratory is selected.

Amended Appendix E Collection, Storage, and Shipment of Bioanalytical Samples
or new wording: 3. Centrifuge the vacutainers for 10 minutes at approximately 1100-1300 **1200** relative centrifugal force (RCF) at approximately 4°C in a refrigerated centrifuge or at ambient temperature. Note: if using a collection device other than Becton-Dickinson, refer to manufacturer's instruction for proper centrifugation force and time

4. Immediately following centrifugation, gently remove plasma from the packed cells. ~~To ensure a more homogeneous sample, all plasma should first be transferred into 1 aliquot. From there, split the plasma evenly between the 2 aliquots.~~ A minimum of approximately 1.2 mL needs to be obtained for each sample. Labeling may include protocol number (TAK-390MR_106), matrix (ie, plasma), analyte (TAK-390MR), enrollment number, nominal day and time, and either "SET 1" (for original sample) or "SET 2" (for duplicate sample).

5. Cap the labeled storage tubes and freeze the plasma samples immediately at approximately -20°C or lower. No more than **45**~~120~~ minutes will elapse between blood collection and freezing the plasma sample.

Instructions for processing and shipping of plasmablood** samples for genotyping analysis**

~~To be determined when laboratory is selected.~~ **Detailed instructions for the handling and shipping of samples will be provided in the Lab Manual**

Rationale for Change:

Updated to reflect the current procedures for plasma samples for pharmacokinetic analysis and to provide the reference to the lab manual for information regarding processing and shipment of blood samples for genotyping analysis.

Change 2: Correct blood volume for genotype analysis and total blood volume.

The change occurs in Section 9.1.8 Procedures for Clinical Laboratory Samples, Section 9.1.12 Sample Collection for Genotype Analysis, and Section 9.4 Blood Volume:

Initial wording: **Section 9.1.8 Procedures for Clinical Laboratory Samples**
All samples will be collected in accordance with acceptable laboratory procedures. The maximum volume of blood at any single visit is approximately 84 mL, and the total volume of blood for the study is approximately 156 mL. Laboratory samples will be taken following a minimum 8-hour overnight fast on the days stipulated in the Schedule of Study Procedures (Appendix A).

Section 9.1.12 Sample Collection for Genotype Analysis

Genotyping and phenotyping analysis for CYP2C19 will be required for all subjects because dexlansoprazole is metabolized by the polymorphic isozyme CYP2C19. On Day 1, one blood sample (approximately 6 mL) will be collected for genotype analysis. Detailed instructions for the handling and shipping of samples will be provided in the Lab Manual.

Section 9.4 Blood Volume

Sample Type	Sample Volume (mL)	Estimated Blood Collection			Total Volume (mL)
		Number of Samples	Treatment Days		
Clinical laboratory tests	20 mL	3	Screening, Check-in (Day -1), Study Exit		60
Genotyping	6 mL	1		Day 1	6
PK blood collection	6 mL	15		Day 1 to 2	90
Total Approximate Blood Sampling Volume					156

The maximum volume of blood at any single day is approximately 84 mL, and the approximate total volume of blood for the study is 156 mL.

Amended or new wording: **Section 9.1.8 Procedures for Clinical Laboratory Samples**
All samples will be collected in accordance with acceptable laboratory procedures. The maximum volume of blood at any single visit is approximately 84 mL, and the total volume of blood for the study is approximately 1562 mL. Laboratory samples will be taken following a minimum 8-hour overnight fast on the days stipulated in the Schedule of Study Procedures (Appendix A).

Section 9.1.12 Sample Collection for Genotype Analysis

Genotyping and phenotyping analysis for CYP2C19 will be required for all subjects because dexlansoprazole is metabolized by the polymorphic isozyme CYP2C19. On Day 1, one blood sample (approximately 62 mL) ~~will be collected~~ for genotype analysis **will be collected into vacutainers containing anticoagulant K₂EDTA according to the schedule in Appendix A. Instructions for sample processing and shipment are provided in Appendix E.**

Section 9.4 Blood Volume

Sample Type	Sample Volume (mL)	Estimated Blood Collection			Total Volume (mL)
		Number of Samples	Treatment Days		
Clinical laboratory tests	20 mL	3	Screening, Check-in (Day -1), Study Exit		60
Genotyping	62 mL	1		Day 1	62
PK blood collection	6 mL	15		Day 1 to 2	90
Total Approximate Blood Sampling Volume					1562

The maximum volume of blood at any single day is approximately 84 mL, and the approximate total volume of blood for the study is 1562 mL.

Rationale for Change:

Updated current blood volume for genotype analysis and overall blood volume.

Amendment 03 to A Phase 1, Single-Center, Randomized, Open-Label, 2-Arm Parallel Group, Single-Dose Study
to Evaluate the Pharmacokinetics of Dexlansoprazole 30 mg and 60 mg Capsules in Healthy Chinese Subjects

ELECTRONIC SIGNATURES

Signed by	Meaning of Signature	Server Date (dd-MMM-yyyy HH:mm 'UTC')
Personally Protected Data	Statistical Approval	29-Nov-2017 15:37 UTC
	Clinical Pharmacology Approval	29-Nov-2017 15:51 UTC
	Clinical Science Approval	29-Nov-2017 16:49 UTC
	Clinical Science Approval	29-Nov-2017 18:21 UTC

3.0 LIST OF ABBREVIATIONS

λ_z	terminal disposition phase rate constant
AE	adverse event
AUC	area under the plasma concentration-time curve
AUC _{last}	area under the plasma concentration-time curve from time 0 to time of the last quantifiable concentration
AUC _∞	area under the plasma concentration-time curve from time 0 to infinity
BMI	body mass index
bpm	beats per minute
CL/F	apparent clearance after extravascular administration
C _{max}	maximum observed concentration
CS	clinically significant
CYP	cytochrome P450
ECG	electrocardiogram
FSH	follicle stimulating hormone
HBsAg	hepatitis B surface antigen
HCV	hepatitis C virus
HIV	human immunodeficiency virus
MedDRA	Medical Dictionary for Regulatory Activities
NCS	not clinically significant
PK	pharmacokinetics
PT	preferred term
PTE	pretreatment event
SAE	serious adverse event
SOC	system organ class
t _{1/2z}	terminal disposition phase half-life
TEAE	treatment-emergent adverse event
t _{max}	time of first occurrence of C _{max}
V _{z/F}	volume of distribution during the terminal disposition phase after extravascular administration
WHO	World Health Organization

4.0 OBJECTIVES

4.1 Primary Objectives

The primary objective of this study is to assess the PK after a single dose of dexlansoprazole 30 and 60 mg delayed-release capsules in healthy Chinese subjects.

4.2 Secondary Objectives

The secondary objective of this study is to evaluate the safety and tolerability of dexlansoprazole following oral administration of a single 30 or 60 mg dexlansoprazole delayed-release capsule.

4.3 Study Design

This is a phase 1, open-label, single dose, 2-arm parallel study to assess the PK of a single oral dose of dexlansoprazole 30 and 60 mg delayed-release capsules. Forty subjects will be enrolled in the study, 20 subjects in Group 1 and 20 subjects in Group 2 ([Table 4.a](#)).

Table 4.a Parallel Groups

Group	Regimen
1	A single oral dose of dexlansoprazole 30 mg delayed-release capsule
2	A single oral dose of dexlansoprazole 60 mg delayed-release capsule

A schematic of the study design is included as [Figure 4.a](#).

Figure 4.a Schematic of Study Design

Pretreatment Period		Treatment Period		Follow-Up
Screening	Check-in	Dexlansoprazole Delayed-Release Capsule Single Dose (30 or 60 mg)	Discharge/Study Exit/Premature Termination	Follow-up Site/ Telephone Visit
Days -28 to -2	Day -1	Day 1	Day 2	5 to 10 days postdose
←————Confinement to Clinic————→				

Note: A follow-up site/telephone visit will be made for collection of adverse events, serious adverse events, and concomitant medications taken since final dose.

Subjects will fast for a minimum of 8 hours prior to dosing. On Day 1, breakfast will be served 1 hour postdose. Subjects may consume water ad libitum except for 1 hour before and 1 hour after drug administration. Dosing will commence at approximately 8:00 am on Day 1. Study drug will be administered with 240 mL of water. Subjects must drink all of the water provided with the dose.

5.0 ANALYSIS ENDPOINTS

5.1 Primary Endpoint

The primary endpoints for this study are the PK parameters of dexlansoprazole following a single oral dose of dexlansoprazole 30 and 60 mg delayed-release capsules:

- C_{\max} .
- Area under the plasma concentration-time curve from time 0 to time of the last quantifiable concentration (AUC_{last}).
- Area under the plasma concentration-time curve from time zero to infinity (AUC_{∞}).

5.2 Additional Endpoints

- Time of first occurrence of C_{\max} (t_{\max}).
- Terminal disposition phase rate constant (λ_z).
- $t_{1/2z}$.
- Volume of distribution during the terminal disposition phase after extravascular administration (V_z/F).
- CL/F .

5.3 Safety Endpoints

Safety endpoints include treatment-related AEs, clinical laboratory tests (hematology, serum chemistry, and urinalysis), vital sign measurements, electrocardiograms (ECGs), and physical examinations.

6.0 DETERMINATION OF SAMPLE SIZE

No formal sample size calculations were conducted. A sample size of 40 subjects, 20 subjects per parallel group, will be used in this study. This sample size is deemed to be sufficient for the assessment of the PK of dexlansoprazole 30 and 60 mg delayed-release capsules in the Chinese population.

7.0 METHODS OF ANALYSIS AND PRESENTATION

7.1 General Considerations

Statistical analysis will be performed using SAS® software (SAS Institute, Inc., Cary, North Carolina) Version 9.2, or later.

All study-related raw data for enrolled subjects, including derived data, will be presented in data listings. Continuous data will be summarized using number of subjects, mean, standard deviation, median, minimum, and maximum. Categorical data will be summarized using the number and percentage of subjects for each category where appropriate.

7.2 Data Handling Conventions

7.2.1 Premature Withdrawal

The investigator may discontinue a subject's study participation at any time during the study when the subject meets the study termination criteria. In addition, a subject may discontinue his or her participation without giving a reason at any time during the study. Should a subject's participation be discontinued, the primary criterion for termination must be recorded.

Discontinued or withdrawn subjects will not be replaced after enrollment. All available data from subjects who were withdrawn from the study will be listed and all available planned data will be included in summary.

7.2.2 Handling of Missing Data

No imputation will be used for Missing data.

7.2.3 Handling of Missing/Partial Date

Completed missing start or end dates will remain missing, with no imputation applied.

Partial dates will be imputed using below convention:

- If the partial date is a start date, impute as the first day as the month (only missing day) /year (missing both month and day).
- If the partial date is an end date, impute as the last day as the month (only missing day) /year (missing both month and day).
- If the partial date is in the same month (only missing day) or same year (missing both month and day) as the study treatment, and the imputed start date of an adverse event (not pretreatment event) is prior to the start of study treatment, then the start date of study treatment will be assumed to be the start date. The AE will then be considered as start on treatment (worst case scenario).

The recorded partial date will be displayed in the listings.

7.2.4 Definition of Baseline and Change from Baseline

Baseline is defined as the last non-missing measurement prior to first dose of study drug.

CONFIDENTIAL

The change from baseline will be calculated by subtracting the baseline values from the individual post-baseline values. If either the baseline or post-baseline value is missing, the change from baseline is set to missing as well.

7.2.5 Definition of Study Days

Study day will be calculated relative to the date of the first dose of study drug in the study. The study day prior to the first dose of study drug will be calculated as:

Date of assessment/event – date of first dose of study drug

The study day on or after the first dose of study drug will be calculated as:

Date of assessment/event – date of first dose of study drug + 1.

AEs that start more than 30 days after the last dose of study drug will be listed, but excluded from the summaries and analyses.

7.3 Analysis Sets

Enrolled Subjects Set (EPS): All enrolled subjects who are enrolled will be included, which will be used in the analysis of disposition, medical history, protocol deviation, etc.

Safety Analysis Set (SS): All subjects who are enrolled in the study and take at least 1 dose of study drug will be included, which will be used in the demographic summary and safety data analysis.

PK Analysis Set (PAS): All subjects who receive at least 1 dose of study drug and have at least 1 measurable plasma concentration of dexlansoprazole will be included, which will be used in PK data analysis.

7.4 Disposition of Subjects

Disposition of all screened subjects will be tabulated (count and percent). Primary reasons for screen failure will be summarized and will be presented in a data listing. There will be no inferential analysis of subject disposition data.

Disposition of all enrolled subjects will be tabulated by dexlansoprazole dose groups and overall:

- All subjects received at least one dose of study drug.
- Subjects who completed the study.
- Subjects who prematurely discontinued study.

Primary reasons for discontinuation of study, as entered on the electronic case report form (eCRF), will be tabulated. The date of first dose, date of last dose, duration of treatment and the reason for premature discontinuation of study drug/study visit will be presented for each subject in listings.

7.5 Protocol Deviation

A summary of the number and percentage of subjects with a significant protocol deviation by type of deviation will be provided using enrolled subjects set by dexlansoparzole dose groups and overall. Individual subject listings of significant protocol deviations will be provided.

7.6 Demographic and Baseline Characteristics

Demographic and baseline characteristics variables will be summarized by dose group and overall using the safety analysis set.

For continuous variables (age, weight, height, and body mass index [BMI]), summary statistics will be generated.

For categorical variables (gender, ethnicity, race, smoking status of the subject at Screening, caffeine consumption and alcohol history), the number and percentage of subjects in each category will be presented.

7.7 Medical History and Concurrent Medical Conditions

Medical history include any significant conditions or diseases that stopped at or prior to signing of informed consent. Concurrent medical conditions are those significant ongoing conditions or diseases that are present at signing of informed.

Medical history and concurrent medical conditions will be presented in a data listing only.

7.8 Medication History and Concomitant Medications

Medication history information to be obtained includes any medication relevant to eligibility criteria stopped at or within 28 days prior to signing of informed consent. Concomitant medications are recorded on the eCRF and include any medications, other than study drug, taken at any time between informed consent and the end of the study. They may be prescribed by a physician or obtained by the subject over the counter.

All medication history and concomitant medications will be coded by therapeutic classification, sub-classification, and medication using the World Health Organization Drug Dictionary (WHO Drug).

All medication history and concomitant medications will be listed by site (study center) and subject number. The listings will contain subject identifier, treatment, World Health Organization Drug Dictionary (WHO Drug) preferred medication name, dose, unit, frequency, route, start date, stop date, whether the medication was ongoing, and reason for use. No summary or inferential statistics will be presented.

7.9 Study Drug Exposure and Overdose

Study drug administration and overdose information will be listed. Standard meal information will also be presented. Summaries of PK data will be provided by dose group. No other summary statistics for the extent of exposure to study drug or compliance calculations will be performed for this study.

7.10 Pharmacokinetic Analysis

All PK summaries will be based on the PK set. PK parameters of dexlansoprazole will be derived using non-compartmental analysis methods. They will be determined from the concentration-time data for all evaluable subjects. Actual sampling times, rather than scheduled sampling times, will be used in all computations involving sampling times.

Serial blood samples for determination of dexlansoprazole concentrations will be collected on Day 1 (within 30 minutes before dosing) and at 0.5, 1, 1.5, 2, 3, 4, 5, 6, 7, 8, 10, 12, 16, and 24 hours post dose. The concentration of dexlansoprazole in plasma will be summarized by scheduled sampling time points and dose group using descriptive statistics. Individual plasma concentration data will be presented in a data listing. Subject phenotypes will be listed with the concentrations.

The PK parameters of dexlansoprazole will be determined below from the concentration-time profiles for all evaluable subjects. Actual sampling times, rather than scheduled sampling times, will be used in all computations involving sampling times. The following PK parameters will be calculated:

Symbol/Term	Definition
Plasma	
AUC _{last}	Area under the plasma concentration-time curve from time 0 to time of the last quantifiable concentration.
AUC _∞	Area under the plasma concentration-time curve from time 0 to infinity.
C _{max}	Maximum observed concentration.
CL/F	Apparent clearance after extravascular administration.
λ _z	Terminal disposition phase rate constant.
t _{1/2z}	Terminal disposition phase half-life.
t _{max}	Time of first occurrence of C _{max} .
V _z /F	Apparent volume of distribution during the terminal disposition phase after extravascular administration.

Descriptive statistics (number of subjects, arithmetic mean, SD, %CV, median, minimum and maximum) by dose groups will be provided for dexlansoprazole plasma PK parameters. Geometric means will be calculated for Cmax and AUCs. Individual plasma PK parameters will be presented in a data listing. Subject phenotypes will be listed with the PK parameters.

No inferential statistical analysis will be performed. Additional summaries by phenotypes may be performed if there are sufficient number of subjects for each phenotype. More information please refer to separate clinical pharmacology analysis plan (CPAP).

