Dexlansoprazole is primarily metabolized by the cytochrome P450 (CYP) enzymes CYP3A4 and polymorphic CYP2C19 [1]. The CYP2C19 poor metabolizer (PM) phenotype is present in 12% to 23% of the Asian population, and the prevalence of CYP2C19 PMs in Chinese subjects is similar to that of other Asian populations [3]. Study TAK-390MR/CPH-002 assessed the PK of multiple doses of dexlansoprazole 30 and 60 mg capsule doses in male Japanese PM and extensive metabolizer (EM) subjects. In the Japanese PMs, dexlansoprazole $t_{1/2z}$ was approximately 3 times longer than in EMs, and apparent clearance after extravascular administration (CL/F) in the EMs was approximately 4-times greater than PMs. Although the availability of PK data in PMs in the Caucasian and African American population is limited, it is expected that dexlansoprazole exposure in these races will be affected by CYP2C19 phenotypes as well.

The majority of the dexlansoprazole capsule phase 1 studies were conducted in the United States. As development of dexlansoprazole expands to other countries, additional studies are needed to bridge between the data acquired previously in North American and Asian populations.

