9.1.14 Pharmacokinetic Parameters

The PK parameters of dexlansoprazole will be determined from the concentration-time profiles for all evaluable subjects. Actual sampling times, rather than scheduled sampling times, will be used in all computations involving sampling times. The following PK parameters will be calculated from plasma concentration values:

Symbol/Term	Definition
Plasma	
AUC _{last}	Area under the plasma concentration-time curve from time 0 to time of the last quantifiable concentration.
AUC _∞	Area under the plasma concentration-time curve from time 0 to infinity.
C _{max}	Maximum observed concentration.
CL/F	Apparent clearance after extravascular administration.
λ _z	Terminal disposition phase rate constant.
t _{1/2z}	Terminal disposition phase half-life.
t _{max}	Time of first occurrence of C _{max} .
V _z /F	Apparent volume of distribution during the terminal disposition phase after extravascular administration.

Other parameters may be calculated, if appropriate.

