13.0 STATISTICAL METHODS

13.1 Statistical and Analytical Plans

A statistical analysis plan (SAP) will be prepared and finalized prior to database lock. This document will provide further details regarding the definition of analysis variables and analysis methodology to address all study objectives.

The targeted review plan will be conducted prior to database lock. This review will assess the accuracy and completeness of the study database, subject evaluability, and appropriateness of the planned statistical methods.

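### Does the undefined term *evaluable* in SAP 7.10 leave primary PK parameters from incomplete profiles without a usable rule?

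*SAP*

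**What the plan says.** Four statements bear on which subjects supply the primary PK parameters (Cmax, AUClast, AUC∞).

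- SAP 7.10, on summaries: "All PK summaries will be based on the PK set".
- SAP 7.10, on derivation: "They will be determined from the concentration-time data for all evaluable subjects". Protocol 9.1.14 agrees: "The PK parameters of dexlansoprazole will be determined from the concentration-time profiles for all evaluable subjects". The term is defined in neither document.
- SAP 7.3, on the PK set: "All subjects who receive at least 1 dose of study drug and have at least 1 measurable plasma concentration of dexlansoprazole will be included". It sets no condition on how complete the profile is.
- SAP 7.2.1, on withdrawn subjects: "all available planned data will be included in summary". SAP 7.2.2 rules out imputation, and withdrawn subjects are not replaced.

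Two further places are relevant. Protocol 13.1 plans a review before database lock: "This review will assess the accuracy and completeness of the study database, subject evaluability, and appropriateness of the planned statistical methods". SAP 7.10 ends by sending the reader to a separate clinical pharmacology analysis plan (CPAP), which is not among the documents reviewed.

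**The concern.** Take a subject who is dosed and leaves before the 24-hour sample. One measurable concentration puts that subject in the PK set, and 7.2.1 appears to put a shortened AUClast into the summary. The *evaluable* wording could remove the same value. No order of precedence is written down.

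The parameters are primary endpoints, each dose group has 20 subjects, and Protocol 6.2 intends the results to be bridged to North American and Japanese data, so the group means are the main product. A truncated profile also stays truncated: Protocol 9.1.13.1 takes no PK sample at an early termination visit unless one was scheduled. If the choice were made after seeing the values, the reported mean could depend on it.

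**Working it through.** **Step 1: the passages side by side.**

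| Place | Step it governs | Condition |
|---|---|---|
| SAP 7.10 and Protocol 9.1.14, *evaluable* | deriving a parameter | profile judged adequate (undefined) |
| SAP 7.10 with 7.3, PK set | summarising values | one dose, one measurable concentration |
| SAP 7.2.1 with 7.2.2 | withdrawn subjects | data that are available; nothing imputed |

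In this order the rules do not collide. A parameter is derived where the profile supports it, and derived values are summarised over the PK set. A parameter that was not derived is not available, so 7.2.1 has nothing to add and n falls for that parameter. The open case is narrow: a value that could be computed, such as AUClast from a short profile, but is dropped as not evaluable.

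**Step 2: size of that case.** The plan has no figure to reproduce beyond 20 + 20 = 40, because no formal sample size calculation was made.

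Let one of 20 subjects keep a fraction f of the full AUClast (f is assumed). The group geometric mean is multiplied by f^(1/20):

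- f = 0.10: 0.891 (−11%)
- f = 0.25: 0.933 (−7%)
- f = 0.50: 0.966 (−3%)
- f = 0.75: 0.986 (−1%)

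For a typical subject the arithmetic mean is multiplied by (19 + f)/20, which is 0.955 at f = 0.10 and 0.988 at f = 0.75. With two such subjects the geometric factor is f^(2/20), from 0.794 to 0.972.

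**Step 3: metabolizer status.** Protocol 4.1 gives a half-life of 1 to 2 h, about 3 times longer in poor metabolizers (PMs), so 3 to 6 h. It says apparent clearance "in the EMs was approximately 4-times greater than PMs", so PM exposure is taken as 4 times that of everyone else. A PM prevalence of 12% to 23% gives 2.4 to 4.6 PMs per 20; 2 to 5 are used, the upper end being slightly above the cited range.

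Excluding one subject when the group has m PMs changes the geometric mean by:

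- a PM: 4^((m−1)/19) / 4^(m/20) − 1. For m = 2, 3, 5 this is −6.4%, −6.0%, −5.3%.
- a non-PM: 4^(m/19) / 4^(m/20) − 1. For m = 2, 3, 5 this is +0.7%, +1.1%, +1.8%.

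Keeping the subject requires f by stopping time. That rests on inputs the documents do not give: one or two release phases, lag times, absorption rates of 0.6 to 1.3 per hour, a quantification limit at 0.2% to 1% of Cmax, and no other variability.

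- Non-PM leaving at 2 h: f 0.06 to 0.35, change −13% to −5%.
- Non-PM leaving at 12 h: f 0.93 to 1.00, change −0.4% to 0.
- PM leaving at 8 h: f 0.40 to 0.80, change −4.5% to −1.1%.
- PM leaving at 12 h: f 0.66 to 0.94, change about −2% to −0.3%.

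Under the same assumptions Cmax keeps 0.25 to 1.00 of its full value if sampling stops at 2 to 4 h, and all of it from 6 h on.

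**Step 4: scale.** With 20 subjects and an assumed geometric CV of 30% to 60%, the 95% interval factor for a group geometric mean is exp(2.093 × √(ln(1 + CV²)/20)), which is 1.15 to 1.30. A lower limit of 1/1.15 is −13%. Only departures within the first few hours approach ordinary sampling error.

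**The case for a change.** The strongest case for acting is this. The protocol leaves the definition of analysis variables to the SAP, and the SAP leaves this term open. The evaluability review has no stated criteria, and nothing says it must precede sight of the concentrations in an open-label study. The CPAP reference follows the sentence on phenotype summaries, so its scope is unclear. Neither blanket reading is safe either: excluding is closer to complete data for a non-PM who leaves at 2 h (+0.7% to +1.8%, against −5% to −13% if kept), while keeping is closer for a PM who leaves at 8 h (−1.1% to −4.5%, against −5.3% to −6.4% if excluded). A definition would cost a few sentences.

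The absence of a definition stands, and so does the reversal by metabolizer status, given the assumed kinetics. A contradiction does not stand, because the statements govern different steps. Nor can it be said that no rule exists anywhere, since the CPAP may hold one.

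The reversal also weakens the case for a general rule. A completeness cut-off would need a nominal time that nothing in the documents supports. A test that sampling passed the peak cannot be verified on a truncated profile if the formulation releases drug in two phases, because a later peak may be unobserved.

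**Conclusion.** No change to the plan follows. This is a gap in detail that the analysts can fill sensibly: derive what each profile supports, settle evaluability at the planned pre-lock review, and summarise the available values over the PK set. SAP 7.10 already reports the number of subjects with the parameter statistics and lists individual concentrations, parameters and phenotypes. An exclusion would therefore be visible, and a reader could recompute the mean either way.

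The size is zero if nobody leaves early. One early departure in 20 moves the AUClast geometric mean by about 1% to 11% for f between 0.75 and 0.10, and by up to about 13% for a non-PM leaving at 2 h. By 12 h, keeping the value costs about 2% at most. Departure that early is unlikely with one observed dose and confinement through Day 2, and no inferential analysis depends on the result.

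The figures by stopping time rest on assumed absorption and quantification limits. The exclusion figures rest on the protocol's fourfold clearance ratio applied to all non-PMs and on 2 to 5 PMs per group. The conclusion that the passages are compatible needs none of these assumptions.
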